Roles and responsibilities: The *headquarters* acting as the coordinating centre is located at the Royal Free Hospital in London, UK run by [name] [name], [name] and the Management Committee. The *Chief Investigators* of LiverGroup.org are [name] from the University of Zaragoza, Spain and [name] from the Royal Free Hospital, London, UK. The complete list of the LiverGroup.org Team is available at: <https://livergroup.org/?q=team>. The responsibilities of the members of the *Management Committee* are, among others facilitating the group's decision-making processes, distributing newsletters, announcements and invitation letters, safeguarding and applying regulations, arranging regular committee and general meetings of the group, recording decisions and tasks clearly, and providing support to the collaborators. The *Steering Committee* Members are: [name] (Greece), [name] (Germany), [name] (Brazil), [name] (Chicago), [name] (Japan), [name] (Norway) [name] (Canada), [name] (Switzerland), [name] (Netherlands), [name] (Turkey) and [name] (Germany). Their responsibilities include, among others overseeing and controlling the scientific part of the project and giving strategic direction and support to the members of the management committee. The Members of the *Steering Committee* have approved the study design and protocol of the LiverGroup.org Study. The *Country Leaders* are responsible for recruiting centers within their country/region. Additionally, *Auditors* (data monitors) will be assigned to monitor the adherence to the protocol as well as auditing the quality of data collection of the different participating centers.

Summary

Introduction: Liver surgery was associated with at least 10% mortality in the 1970's. The safety of liver surgery has dramatically improved since with a mortality now of around 1-2%. Individual centres put the bar even higher and postulate that a perioperative mortality close to 0% should be the standard of major liver resection. Despite these claims, epidemiological studies paint a different picture again with a mortality rate of 6%.

Eligibility: Any surgeon performing liver resections is eligible to participate in LiverGroup.org. All consecutive cases must be included and there are no minimum patient numbers per centre. Liver transplantation is excluded.

Time period and team members: Each participant may form a team of 3 members in total. There will be 3 months of prospective patient enrolment and 3 months follow up within a 12-month frame (Jan – Dec 2019).

Inclusion criteria: All liver resections will be included:

- All indications (including benign and living donor resections), all co-morbidities
- Open, laparoscopic or robotic
- Single wedge resections to extended liver resections
- Single or two-stage hepatectomies
- Procedures with liver volume enhancement such as PVE, PVL, ALPPS.
- Resections involving cold perfusion (ex-situ and ante-situ)
- There are no exclusion criteria as related to indication, age or comorbidities.

Exclusion criteria:

- Liver transplantation
- CT-guided RFA, MWA, etc.
- Liver biopsies

Audit Standard: An audit of the consecutivity, intent-to-treat and completeness of data entered will be performed by random selection of at least 30% of the contributing surgeons. A member of LiverGroup.org will be assigned to audit one fellow surgeon of LiverGroup.org to perform a validation of the number of deaths and of the death dates.

Outcomes: the primary endpoint of the analysis will be 90-day mortality. Secondary endpoints will be liver failure, complications, and length of stay and incidence of re-hospitalisation.

Data ownership: The study sponsors, the Royal Free Hospital London and University of Zaragoza, will act as the custodians of the data. The steering and management committees together will decide after the publication of the main report about requests regarding secondary analysis and will consider all such requests based on quality and the validity of the proposed project and decide by majority decision.

Authorship: A single analysis and reporting without hierarchical authorship (no first author, no last author) is planned at the end of the study (a “pure” group author publication) to reflect the collaborative effort.

Register: Please register your interest for participation at:

<https://LiverGroup.org/?q=register>

Introduction

The safety of major liver surgery, defined as resection of four or more hepatic segments has improved significantly in recent decades with mortality rates improving from 10% in the 1970's¹ to 1-2% currently.²⁻⁵ Some individual centres are now reporting perioperative mortality rates approaching 0%,^{4,6} yet epidemiological studies suggest much higher mortality rates of up to 6%.⁷ the reasons for this discrepancy are not completely understood.

Complexity and extent of liver surgery, patient selection and both centre and surgeon experience are all cited factors which may influence outcomes following major liver surgery. A large, single-centre analysis of outcomes following liver surgery found that the number of hepatic segments resected and operative blood loss were the only two predictors of both perioperative morbidity and mortality.⁵ The authors suggest that whilst 'complex liver resections' defined as liver surgery with one or more major extrahepatic procedure, were associated with a higher mortality in conjunction with major hepatectomies, complexity had no impact on mortality when performed with minor hepatectomies, thus highlighting the importance of future liver remnant percentage (FLR) which has since been repeatedly demonstrated.^{8,9} Induction of regeneration prior to resection using portal vein embolization, portal vein ligation or Associating Liver Partition and Portal vein ligation for Staged hepatectomy (ALPPS) are evolving strategies to mitigate the adverse outcomes associated with a major liver surgery. Such staged approaches to major liver resections are associated with a perioperative mortality of over 5% even in the most experienced centers¹²⁻¹⁴ with the ALPPS procedure reported to have a mortality of 12% in voluntary registry studies.¹⁵ Whether such strategies improve the safety of major liver surgery, or instead allow a more aggressive approach to resection of lesions previously deemed unresectable is contentious.

At the extreme end of complexity are ex-situ and ante-situ resections. The largest series of standardized in-situ hypothermic perfusion for patients with tumours involving the vena cava and the hepato-caval junction identified an overall mortality rate of 20%.¹⁸

An open debate and ultimately consensus amongst the HPB surgical community is required to address the delicate balance between improving mortality of liver surgery whilst developing approaches to treat the most challenging lesions. To inform this debate a robust prospective audit examining the current international experience and outcomes is required. Existing registry studies are based on national (French Liver surgery registry, Scandinavian liver surgery registry LiverMET Survey SweLiv²¹, Italian laparoscopic liver surgery registry²²) or

international collaborations (e.g. the ALPPS registry initiated in 2012, [www.ALPPS.net¹⁵](http://www.ALPPS.net)) are commendable attempts to provide valid data. They have however either not been international in scope, proprietary in character or have underestimated the true incidence of morbidity and mortality due to voluntary and selective reporting of patients or lack of monitoring of data entry. Large single centre studies both in Europe and the US with high quality retrospective databases have provided the most robust data,^{3,5,6} but across a long enrolment periods and with a considerable era and centre bias. Furthermore, series from high volume, single centre, specialised units represents only the 'tip of the iceberg' of practice of liver resection worldwide.

The International Liver Surgery Outcomes Study – LiverGroup.org aims to measure the true worldwide practice of Liver surgery and associated outcomes by recruiting multiple international centres, committing to consecutive patient registration per surgeon and undergo rigorous data validation. It is hoped that these data will provide a more appropriate guide to inform surgeons and patients to assess which level of complexity should be routinely offered for high tumour burden and anatomically difficult scenarios.

Methods

Participants, interventions and outcomes

Study setting

This will be an International Liver Surgery Outcomes Study where all centres performing liver surgery world-wide will be able to participate. The current preliminary list of study sites is available at <https://livergroup.org/?q=team>.

Eligibility criteria

All patients undergoing liver resection by single surgeons at their respective centres are eligible for study inclusion. The *inclusion criteria* are patients 18 years of age or older, any indication for surgery, including benign and living donor resections, open, laparoscopic, hybrid or robotic approaches. Furthermore, any extent of liver resection is included, from single wedge resections to extended liver resections. Procedures with liver volume enhancement such as PVE, PVL, ALPPS, resections involving cold perfusion (ex-situ and ante-situ) are also included. The *exclusion criteria* are patients undergoing liver transplantation, liver biopsies or image-guided liver ablation alone.

Outcomes

The *primary objectives* of LiverGroup.org is to develop a non-proprietary international data set on the **morbidity** and **mortality** following liver resections among international surgeons. Morbidity will be recorded according to the Clavien-Dindo Classification of Surgical Complications, the FABIB Liver Surgery-Specific Classification and the novel Comprehensive Complication Index® (CCI®). Mortality will be captured until the 90th postoperative day.

The *secondary objective* is to identify independent risk factors for morbidity and mortality using multivariable regression models.

Participant timeline and study duration

The enrolment period will last 3 months and a minimum of 3 months period is required for follow-up of each patient. Surgeons may start enrolment at any time within the 12-month enrolment time frame: 1st of January 2019 until the 31st of December 2019. The Management Committee may decide to prolong the patient enrolment if deemed necessary.

Sample size

The study aims for the maximum number of patients it will be able to recruit and has no power calculation for specific outcomes. Assuming a 2.5% 90-day mortality rate, at least 2000 patients will have to be recruited to be able to perform a meaningful multivariate analysis on independent risk factors postoperative mortality

Recruitment

Surgeons joining LiverGroup.org are encouraged to propose a country or regional leader (north/south etc). This process will be guided by the management committee. The responsibilities of the *Regional* and *Country Leaders* representing each country in the world include, among others to recruit and co-ordinate collaborators in their own country or region as well as to provide additional scientific and administrative support to their collaborators. Additionally, personal contacts of the LiverGroup.org team will be used to recruit centres. Furthermore, the members of the Management Committee are seeking for endorsement of the International Hepato-Pancreato-Biliary Association (IHPBA), European-African Hepato-Pancreato-Biliary Association (E-AHPBA), the American Hepato-Pancreato-Biliary Association (AHPBA), and the Asian-Pacific Hepato-Pancreato-Biliary Association (A-PHPBA).

Data collection, management, and analysis

Study data

Data are “surgeon-based”, not “centre-based”. Surgeons participating in LiverGroup.org are only responsible for their own data. The data will indicate in an anonymized fashion that surgeons belong to a specific centre. Data will be entered using a personalized login assigned to surgeons, their assistants and in some centres, study nurses. The complete dataset of the electronic Case Report Form (CRF) are available at <https://livergroup.org/?q=instructions>.

Each CRF has a unique identifier. A participant may enter data for a colleague or partner under their login, as long as authorization has been granted by the user. If centres are not willing to disclose their identity to the management committee when asked to do so for the purpose of an audit, they are free to have their data excluded from the analysis. Such exclusion will be reported in the final report for transparency while assuring that the data are under control of the individual centre until the final analysis and audit is performed.

Data collection

Data will be entered directly onto the electronic CRF available at <https://livergroup.org/?q=CRF> which includes the unique identifier. Collaborators keep a paper key list connecting the unique database identifier with the patient name in a safe place locked away under their control and their responsibility. If the list gets lost and audit is impossible, the surgeons’ data will be excluded from the final analysis and reported in the final report. The LiverGroup.org management committee cannot identify an individual patient or surgeon or centre without contacting the local PI who entered the data and is in possession of the key to the data.

Data collection methods

The Management Committee currently consists of clinicians who will review data entered, monitor progress and maintain the platform and send reminders to the participants regarding completion of data or questions regarding clarifications. Any collaborator is welcome to join the Management Committee. This practice is introduced to avoid the proprietary use of the collected data by a few “founding members” or “coordinators” or members of an appointed “scientific committee”.

To avoid *selective reporting*, all consecutive patients undergoing liver resections by one individual surgeon over three months are included. In some patients the operation may not run the expected course, be aborted or changed in scope. Intraoperative findings may change the operative plan. These patients should also be recorded in the registry following the principle of intent-to treat to avoid incomplete reporting.

An audit of the consecutively, intent-to-treat, completeness of data entered will be performed by random selection of the contributing surgeons. A member of LiverGroup.org will be assigned to audit one fellow surgeon of LiverGroup.org to perform a validation of the number of and date of deaths. This randomly assigned peer-review by participating centres is entirely novel and has not been routinely performed in similar snapshot studies, to the best of our knowledge. In detail, e.g. a surgeon/monitor from site A will monitor site B while a surgeon/monitor from site B will monitor site C. The monitors themselves may want to carry the costs for the monitoring, but in case that is not possible, LiverGroup.org may help to provide funding from third parties.

As for the quality of the data collected, the electronic CRF is specially designed to force data entry for the important variables (e.g. comorbidities, procedure type, morbidity, mortality, etc.), has minimum and maximum allowed values to avoid typing errors for continuous variables, all categorical data are captured in the form of selection lists and there is a description for important variables within the CRF. Additionally, there are calculators available at LiverGroup.org (e.g. sFLR and conversion of lab values) to ensure uniform data capture. Furthermore, information regarding the Brisbane, Clavien-Dindo, FABIB, BCLC Staging, and Bismuth-Corlette classifications is also available at LiverGroup.org.

All participants will have the opportunity to read study documents available at LiverGroup.org including instructions as well as contact the Management Committee in case they have questions directly through the platform.

Data management

LiverGroup.org is a Clinical Trial Management System (CTMS) built on Drupal 7 that will act as the backbone of our study, by supporting administration, collaboration, communication and information sharing needs among members from several centres worldwide. Anonymised patient data will be stored in two separate secured sites with access given only to the relevant users. There will be regular backups. Furthermore, the CTMS is secured with a Hypertext Transfer Protocol Secure (HTTPS) in combination with a SSL/TLS protocol and an encrypted SQL database.²⁴

The study sponsors, Royal Free Hospital London and University of Zaragoza, will act as the custodians of the data. The steering and management committees together will decide after the publication of the main report about requests regarding secondary analysis and will consider all such requests based on quality and the validity of the proposed project and decide by majority decision.

Statistical methods

The primary endpoint of the analysis will be the 90-day mortality; secondary endpoints will be liver failure by Clavien-Dindo score,²³ the FABIB classification, complications, length of stay and incidence of re-hospitalisation. Descriptive statistics will be performed. Continuous variables will be compared with the Student t test, the Mann-Whitney U test and the Kruskal-Wallis H test or one-way ANOVA as appropriate. Differences among proportions derived from categorical data will be compared using the Fisher test and the Pearson chi-square. Univariate analysis will be performed to test factors associated with post-operative complications and 90-day mortality. Multivariable regression models will be used to identify factors independently associated with these outcomes and to adjust for differences in confounders. Results of the multivariable analyses will be reported as adjusted odds ratios (OR) with 95% confidence intervals. ROC curves and the Youden's index will be used to identify ideal cut-off points for continuous variables. All p values will be 2-sided and considered statistically significant if $p < 0.05$. The statistical analysis will be performed using R version 3.3.2 (R Core Team, GNU GPL v2 License), R Studio version 1.0.44 (RStudio, Inc. GNU Afferro General Public License v3, Boston, MA, 2016) with the graphical user interface (GUI) rBiostatistics.com (rBiostatistics.com, London, UK, 2017).

Monitoring

The management committee will monitor the export database of all CRFs weekly. At least 30% of centre should have undergone on-site peer – monitoring as explained above prior to final analysis.

Safety

This trial involves no risk of bodily harm to patients or investigators. Therefore, adverse events will not be monitored or reported. Data confidentiality will be protected through local anonymization. Anonymization will be monitored and breaches of confidentiality reported. Individual participants are responsible toward their local authorities for breaches in confidentiality.

Ethics and dissemination

Research ethics approval

LiverGroup.org was recognised as an audit in the UK and does not require any ethics approval. The principal investigator in the UK must ensure the recording of data is carried out in accordance with the Research Governance Framework for Health and Social Care; Second Edition, 2005, and its subsequent amendments. The principle investigators in the respective countries must clarify the need for ethics and other regulatory approvals and ensure these are in place prior to data collection. The management committee will collect documentation of the necessary ethics and other regulatory approvals from the respective centres prior to providing electronic access to the CRF. Since this study is effectively a large-scale international clinical audit of anonymized data already recorded in the course of routine patients care, we expect that in most countries no

individual patient consent will be required (see above). For countries where individual consent is required, we will provide an informed consent form in English that may be adjusted to local requirements. Any not enrolled patient due to no patient consent will have to be recorded and reported in the final report. The English version of the patient information and consent form is available at <https://livergroup.org/?q=instructions>.

LiverGroup.org will support all surgeons with their respective institutional review boards/ethics committee applications. Individual modifications to the generic protocol may become necessary.

Declaration of interests

There are no financial and other competing interests of the principal investigators for the overall trial and each study site.

Access to data and dissemination policy

LiverGroup.org is a collaboration of all surgeons contributing data as equal partners. Each surgeon contributing data has access to analysis files of the entire database at any time point and the right to propose analyses and publish data as long as every surgeon contributing data are included as a group author in every publication and have an opportunity to review the data prior to submission. Each collaborator has access to their own data in a form of excel export file without requiring permission or approval by the LiverGroup.org management committee.

One single analysis without hierarchical authorship (no first author, no last author) is planned at the end of the study (a “pure” group author publication) to reflect the collaborative effort. Any member of the group is encouraged to step forward with secondary analyses on specific questions and will have full access to the data. There will be no need for approval of publication of data from The LiverGroup.org collaboration, but all group authors have the right to review the manuscripts and have to be given at least 1 week to be able to review the manuscripts.

References

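### Staged resections have no defined index operation, so the 3-month window pools stage-1 entrants with stage-1 survivors and any mortality figure for staged strategies has no clear meaning

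*Combined protocol and SAP*

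**What the plan says.** Eligibility is wide. The inclusion list in the Summary names "Single or two-stage hepatectomies", and Methods, Eligibility criteria adds: "Procedures with liver volume enhancement such as PVE, PVL, ALPPS, resections involving cold perfusion (ex-situ and ante-situ) are also included".

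Entry is by calendar window. Under Data collection methods, "all consecutive patients undergoing liver resections by one individual surgeon over three months are included".

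The endpoint is stated under Statistical methods: "The primary endpoint of the analysis will be the 90-day mortality". Its horizon is given under Outcomes: "Mortality will be captured until the 90th postoperative day". Participant timeline and study duration adds that "a minimum of 3 months period is required for follow-up of each patient".

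The supplied text has no rule on:
- which operation is day 0 in a staged case;
- a first stage before the window, or a second stage after it;
- how two stages in one patient are linked;
- patients who never reach stage 2.

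Statistical methods plans regression for mortality but does not describe how staged strategies are to be handled.

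**The concern.** With one operation, the 90th postoperative day has one meaning. With two, there are at least two candidate clocks, and the window decides at which stage a patient is first seen. Someone whose first stage fell shortly before the window opened enters at stage 2 as a proven stage-1 survivor. Someone whose first stage falls inside the window enters with the whole risk ahead. If the clock starts at stage 1 and stops at day 90, late deaths after stage 2 are also missed: with six weeks between stages, only 90 − 42 = 48 days after stage 2 are covered.

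This matters because of how the results are to be used. The Introduction says staged approaches are "associated with a perioperative mortality of over 5% even in the most experienced centers", gives 12% for ALPPS in voluntary registries, and treats it as unsettled whether these strategies make surgery safer. It wants the data to guide how much complexity surgeons should offer. A staged-strategy rate that mixes two entry points, on an unspecified clock, would answer that question poorly.

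**Working it through.** The plan states no figure for staged mortality in its own cohort, so there is nothing to reproduce. The check asks how far the observed rate can move from a known true rate.

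**Inputs from the documents.** Strategy mortality M = 0.12 (ALPPS, Introduction). Window W = 3 months, taken as 13 weeks. Overall 90-day mortality 2.5% and N = 2000 (Sample size).

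**Assumptions, not in the documents.** Interval between stages I = 2 to 6 weeks. Share of strategy deaths before stage 2: 50%, 25% or 10%. Staged cases 2% to 10% of the cohort. Stage 1 counts as entry.

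**1. Survivor entry alone** (steady caseload, every stage-1 survivor reaches stage 2, all followed to 90 days after their last stage). Let m1 be stage-1 mortality. Per unit of caseload, W patients enter at stage 1 with risk M, and I(1 − m1) enter at stage 2, contributing I(M − m1) deaths.

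Observed rate = [W·M + I(M − m1)] / [W + I(1 − m1)]

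| Deaths before stage 2 | m1 | I = 2 | I = 4 | I = 6 |
|---|---|---|---|---|
| 50% | 0.06 | 1.68/14.88 = 11.3% | 1.80/16.76 = 10.7% | 1.92/18.64 = 10.3% |
| 25% | 0.03 | 1.74/14.94 = 11.6% | 1.92/16.88 = 11.4% | 2.10/18.82 = 11.2% |
| 10% | 0.012 | 1.776/14.976 = 11.9% | not needed | 2.208/18.928 = 11.7% |

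At a 50% share, stage-2 entrants are 1.88/14.88 = 13% to 5.64/18.64 = 30% of staged records. The shortfall against 12% is 0.7 to 1.7 points at a 50% share, 0.4 to 0.8 at 25%, and 0.1 to 0.3 at 10%. With M = 5% and a 50% share, the rate is 0.70/14.95 = 4.7% to 0.80/18.85 = 4.2%.

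**2. Effect of the clock.** Take a 90-day window, 25% of deaths at stage 1, no drop-out, and deaths after stage 2 clustered early (assumed exponential, mean 25 days). A 30-day interval gives 10.9% counted from the first enrolled operation and 11.3% counted from the last stage. At a 60-day interval these become 9.4% and 10.9%.

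**3. Direction is not fixed.** Let 30% of stage-1 survivors never reach stage 2, with 10% of deaths at stage 1. Stage-2 mortality among those who get there is 0.108/(0.988 × 0.70) = 15.6%, above 12%, so stage-2 entrants now raise the pooled rate. Under a last-stage clock, with g the interval in days, the rate is (0.12 + 0.108·g/90)/(1 + 0.6916·g/90). This is 12.3% at g = 10 and 13.5% at g = 90.

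**4. Overall mortality.** Shift = staged share × staged bias: 0.02 × 0.7 = 0.01 points to 0.10 × 1.7 = 0.17 points. The 95% confidence half-width at 2.5% and N = 2000 is 1.96·√(0.025 × 0.975/2000) = 0.68 points.

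**The case against.** A reader might infer more than the documents support, in four ways.

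- *Staged mortality is certainly understated.* The direction depends on a clock the plan does not state and on drop-out it does not quantify. Step 3 shows a reversal.
- *The rate is roughly halved.* Counting each operation as its own record gives 0.12/1.94 = 6.2%, and looking only at stage-2 entrants gives 0.06/0.94 = 6.4% (both at a 50% share). The first needs operations as the unit, whereas Eligibility criteria, Sample size and Data collection methods all speak of patients. The Summary does say that all resections are included, but as an eligibility statement. The second needs every staged patient to enter at stage 2.
- *The plan breaks its own intent-to-treat rule.* "These patients should also be recorded in the registry following the principle of intent-to treat" concerns operations that are aborted or changed in scope. It is silent on staging, and silence is not contradiction.
- *PVE patients who never reach resection are lost.* PVE is listed among included procedures, so it may itself count as entry. If it does not, all such patients enter at resection; that is selection, not mixing of stages.

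Three further points count against the concern. The complete case report form is linked, not supplied, and may contain stage dates and links. Three months of follow-up is a minimum, so later deaths may be recorded. The primary endpoint is overall mortality, which barely moves. All of this stands and limits the size of the point. What remains is that data fields alone would not define the index date or the denominator, and neither is written down.

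**Conclusion.** The concern holds in a limited form. For two-stage, PVL and ALPPS patients the plan pools two entry points and sets no index operation, so a mortality rate or odds ratio for these procedures cannot be interpreted as the risk of the strategy. On the 12% figure, with 2 to 6 weeks between stages and a quarter to a half of deaths before stage 2, survivor entry lowers the rate by about 0.4 to 1.7 points. A first-stage clock with a long interval lowers it further; a last-stage clock with high drop-out can raise it by up to about 1.5 points. The interval, the split of deaths and the drop-out rate are all assumptions, so the size cannot be fixed from the documents. This is a cheap improvement to subgroup reporting, not a threat to the overall 90-day rate.

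**What to change.** - Keep one linked record per patient, holding the intended strategy and the date of each stage. If the case report form already has these fields, only the analysis wording is needed.
- Set day 0 at the first stage.
- Flag patients whose first stage predates the window. Keep them in the overall cohort, but leave them out of staged-strategy mortality.
- For staged strategies, report 90-day mortality from the first stage, including patients who never reach stage 2. This is the same horizon as for single-stage resection, so the two can be compared.
- As a separate display, report mortality to 90 days after the final stage. It recovers late deaths after stage 2, but gives staged patients a longer time at risk and should not be set against the single-stage rate.
- State separately whether PVE alone counts as entry.

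The cost is a few date fields, a staged denominator smaller by roughly 13% to 30% under the intervals assumed above, and somewhat longer follow-up for a small subgroup.

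### At the stated floor of 2000 patients the mortality model rests on about 50 deaths, so it should be kept small, tied to the observed deaths and fitted by a penalised method

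*Combined protocol and SAP*

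**What the plan says.** The Sample size section of the combined protocol and SAP says the study has no fixed target: "The study aims for the maximum number of patients it will be able to recruit", and it "has no power calculation for specific outcomes". Its one number follows: at an assumed 2.5% 90-day mortality, "at least 2000 patients will have to be recruited to be able to perform a meaningful multivariate analysis on independent risk factors postoperative mortality". It gives no expected number of deaths, number of candidate parameters, events-per-parameter rule or detectable odds ratio.

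Finding independent risk factors for morbidity and mortality is the secondary objective (Outcomes). Under Statistical methods, "Univariate analysis will be performed to test factors associated with post-operative complications and 90-day mortality". Multivariable models reported as adjusted odds ratios are then planned, with ROC and Youden cut-offs for continuous variables and two-sided testing at 0.05. The section lists no covariates, sets no limit on model size and names no method for sparse categories.

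Candidate factors appear elsewhere:
- The Introduction says "Complexity and extent of liver surgery, patient selection and both centre and surgeon experience are all cited factors", and also discusses segments resected, blood loss and future liver remnant.
- The inclusion criteria in the Summary begin "All indications (including benign and living donor resections), all co-morbidities".
- Eligibility criteria lists four surgical approaches, PVE, PVL, ALPPS and cold perfusion.
- Data collection methods makes comorbidities and procedure type compulsory CRF fields.

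**The concern.** The precision of a logistic model for a rare outcome depends on the number of deaths far more than on the number of patients. The plan presents 2000 patients as enough for a mortality risk-factor model but does not convert that to deaths, and it does not say how large the model may be. The factors it discusses outnumber what the floor would comfortably carry, and some categories will be small or have very low risk.

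At stake is the secondary objective. The Introduction hopes that the data will help to show which level of surgical complexity should be routinely offered, so the rare complex procedures are of direct interest in the model. They are also where ordinary maximum likelihood is least stable.

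**Working it through.** **1. The plan's figure.** The documents give no formula for 2000. Expected deaths = 2000 × 0.025 = 50 (95% binomial range 37 to 64). Working backwards, 2000 = (5 parameters × 10 deaths) / 0.025 = (10 parameters × 5 deaths) / 0.025. Both match exactly, but the plan states neither rule.

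**2. Supportable parameters** = deaths / deaths per parameter. The mortality rates are those quoted in the Summary and Introduction, plus the assumed 2.5%.

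| Mortality | Deaths in 2000 | Parameters at 10 deaths each | Parameters at 5 deaths each |
|---|---|---|---|
| 1% | 20 | 2 | 4 |
| 2% | 40 | 4 | 8 |
| 2.5% (plan) | 50 | 5 | 10 |
| 6% | 120 | 12 | 24 |

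**3. Factors named in the documents.** This is my tally, not a covariate list in the plan.
- One parameter each: extent, complexity, centre experience, surgeon experience, blood loss, future liver remnant, comorbidity, cold perfusion (8).
- Approach, four categories: 3.
- PVE, PVL and ALPPS against none: 3.
- Indication, at least malignant, benign and donor: 2.

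That is 11 factors, or 8 + 3 + 3 + 2 = 16 parameters. Fifty deaths give 50 / 11 = 4.5 or 50 / 16 = 3.1 deaths per parameter, both below 5.

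**4. Precision at 50 deaths.** Take an unadjusted binary factor present in 10% of patients with a true odds ratio of 2. Solving 0.9·p0 + 0.1·2p0/(1 + p0) = 0.025 gives p0 = 0.0228, so about 8.9 deaths in 200 patients and 41.1 in 1800.
- SE(log OR) = √(1/8.9 + 1/191.1 + 1/41.1 + 1/1758.9) = 0.377.
- 95% interval: 2 × exp(±1.96 × 0.377), or 0.96 to 4.19. Power is 47%.
- Odds ratio detectable with 80% power (two-sided 0.05): about 2.3 to 2.4 at 20–50% prevalence, 2.85 at 10%, and 3.6 at 5%.

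These figures are before adjustment.

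**5. Categories with no deaths.** P(no death among m patients with risk r) = (1 − r)^m. If no death occurs, the maximum-likelihood log odds ratio against the reference category is minus infinity. The documents give no prevalences, so these are assumptions.
- Living donors, 5% of 2000 = 100 patients, risk 0.1% to 0.5%: 0.999^100 = 0.90 to 0.995^100 = 0.61.
- Cold perfusion, 5 to 20 patients, at the 20% mortality quoted in the Introduction for a hypothermic-perfusion series: 0.8^5 = 0.33 to 0.8^20 = 0.01. Here imprecision is the likelier problem.

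**6. Simulation.** With 2000 patients, about 50 deaths and 16 binary factors at assumed prevalences and effects, about 74% of datasets had at least one rare category with no deaths. Firth estimates stayed finite, with no loss of accuracy for the common factors. The 74% depends on the assumed prevalences and is only an illustration.

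**The case against.** The strongest reply is that nothing in the plan is miscalculated. The figure 2000 equals a conventional 5 parameters at 10 deaths each, it is a floor in a study that seeks as many patients as it can get, and enrolment may be prolonged. No required number of parameters is stated, so a pre-specified model of about five strong, common factors would be workable. All of that stands.

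The choice of 10 deaths per parameter is also only a convention. A shrinkage criterion (target 0.9) gives about 5 to 14 parameters at 2000 patients for an assumed Nagelkerke R² of 0.10 to 0.30. That stands too, and is why one rule should be chosen and stated.

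Four stronger readings are tempting and not supported:
- *The 2.5% is optimistic.* The 1–2% in the Introduction is one end of the quoted range; 6% is the other, and the Introduction says that earlier registries were limited in scope or understated mortality.
- *Sixteen parameters will be fitted.* The tally draws on background and eligibility text, which does not define a model.
- *Covariates will be chosen on univariable p-values.* Univariable and multivariable analyses are both planned, but no selection rule is given.
- *All adjusted odds ratios will be inflated.* The simulation did not show overstatement of 20 to 28% for common factors. Categories with a few deaths still have finite estimates; only those with none (or all) do not.

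**Conclusion.** The concern holds as a cheap improvement worth making. It does not show that the sample size is wrong. At the floor and at 2.5% mortality the study expects about 50 deaths, enough for about 5 parameters at 10 deaths each or 10 at 5 each. The named factors come to roughly 11 to 16 parameters, so a model holding them all would fall below 5 deaths per parameter. Ordinary logistic regression would then give wide intervals, and an infinite odds ratio wherever a category has no deaths.

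A reader might infer that 2000 patients cannot deliver a meaningful risk-factor analysis. The documents do not support that: they set no model size, 2000 is a minimum, and 20 to 120 deaths are possible across their own mortality range. The conclusion rests on the 2.5% assumption, on conventions that the plan does not state, on my tally of factors and, for the zero-death categories, on assumed prevalences. It concerns the secondary objective; the 90-day mortality estimate itself is unaffected.

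**What to change.** **Sample size.** State that 2000 patients at 2.5% mortality give about 50 deaths and so support only a small mortality model, about 5 parameters at 10 deaths each. Use that one sizing rule throughout.

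**Statistical methods.** For the mortality model:
- before database lock, list the covariates in an order set on clinical grounds, not by univariable p-values, and limit the number of parameters by the observed deaths under the same rule;
- fit by Firth-penalised logistic regression with profile-likelihood intervals;
- collapse categories with no or almost no deaths, or report them descriptively.

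Because the limit follows the observed deaths, it works whether recruitment stops at 2000 or goes well beyond.

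**Cost.** Rewording in two sections and a standard R package; no extra patients. Fewer factors can be called independent predictors of death, and penalised estimates for very sparse categories are pulled towards no effect, which the report should say.
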